OUTPUT: L:\DEV\755\71875502\SAS\OUT\XXXX
Page 1 of N

NOVUM PHARMACEUTICAL RESEARCH SERVICES
STATISTICAL ANALYSIS PLAN

Ketoconazole Cream 2%

Protocol / Study No. 71875502

L16.2.7.2 Listing of Pre-treatment Adverse Events

Patient Screening	Patient Randomization Number	Body System / MedDRA Term / AE Term	Treatment Area	Start /End Date/ Ongoing	Severity	Relationship to Study Drug	Outcome	Action Taken/ Other Action Taken	SAE Taken
xx-xxx	xxxx	Nervous system disorders / Headache / Headache	No	mm/dd/yyyy / mm/dd/yyyy	Mild	Related	Recovered	Dose Not Changed/ None	No

PROGRAM: L:\DEV\755\71875502\SAS\PGM\XXXX
Created on: ddmmmyy hh:mm

OUTPUT: L:\DEV\755\71875502\SAS\OUT\XXXX
Page 1 of N

NOVUM PHARMACEUTICAL RESEARCH SERVICES
STATISTICAL ANALYSIS PLAN

Ketoconazole Cream 2%

Protocol / Study No. 71875502

L16.2.8.1 Listing of Pregnancy Test Results

Treatment Group	Patient Screening Number	Patient Randomization Number	Visit 1	Visit 2	Visit 3 / Early Termination
Test	xx-xxx	xxxx	Negative	Negative	Negative

Reference
Placebo

Test: Ketoconazole Cream 2% (Encube Ethicals Pvt Ltd)
Reference: Ketoconazole Cream 2% (G&W Laboratories Inc.; Registrant: Teva Pharmaceuticals USA Inc.)
Placebo: Placebo Cream (Test vehicle) (Encube Ethicals Pvt Ltd)

PROGRAM: L:\DEV\755\71875502\SAS\PGM\XXXX
Created on: ddmmmyy hh:mm

OUTPUT: L:\DEV\755\71875502\SAS\OUT\XXXX
Page 1 of N

NOVUM PHARMACEUTICAL RESEARCH SERVICES
STATISTICAL ANALYSIS PLAN

Ketoconazole Cream 2%

Protocol / Study No. 71875502

L16.2.8.2 Listing of Vital Signs

Treatment Group	Patient Screening Number	Patient Randomization Number	Visit	Systolic BP (mmHg)	Diastolic BP (mmHg)	Pulse Rate (beats/min)	Respiration Rate (breaths/min)	Temperature (F)
Test	xx-xxx	xxxx	Visit 1	120	70	84	18	98.6
			Visit 2	140	100	74	18	97.0
			Visit 3	140	100	74	18	97.0

Reference
Placebo

Test: Ketoconazole Cream 2% (Encube Ethicals Pvt Ltd)

Reference: Ketoconazole Cream 2% (G&W Laboratories Inc.; Registrant: Teva Pharmaceuticals USA Inc.)

Placebo: Placebo Cream (Test vehicle) (Encube Ethicals Pvt Ltd)

PROGRAM: L:\DEV\755\71875502\SAS\PGM\XXXX

Created on: ddmmmyy hh:mm

OUTPUT: L:\DEV\755\71875502\SAS\OUT\XXXX

Page 1 of N

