8.3 Scientific and Statistical Considerations

Ketoconazole is not considered to be sufficiently absorbed from the skin to provide measurable systemic concentrations.⁹ The 21 Code of Federal Regulations Sections 320.24 (Revised April 1, 2014) requires that in-vivo pharmacokinetic testing in humans is the preferred method in evaluating bioequivalence. However, circumstances for which measurement of the active moieties in biological fluids is not possible, a pharmacodynamic response study indicative of clinical efficacy can be considered.^{10,11} Therefore, a comparative clinical endpoint study is considered the most appropriate method to evaluate the clinical (therapeutic) effect of two ketoconazole topical cream formulations.

Sample size estimations for this study are based on studies conducted for Teva Pharmaceuticals Abbreviated New Drug Application (ANDA) #075-581 for Ketoconazole Cream 2%.¹

CONFIDENTIAL PROTOCOL

A Randomized, Double-Blind, Vehicle-Controlled, Parallel-Design, Multiple-Site Clinical Study to Evaluate the Therapeutic Equivalence of Ketoconazole Cream 2% (Encube Ethicals Pvt Ltd) to Ketoconazole Cream 2% (G&W Laboratories Inc.) in the Treatment of Tinea Pedis

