8. STATISTICAL ANALYSIS METHODS

If not otherwise specified, statistical significance is defined as $p < 0.05$ and is two-tailed. Data will be summarized with respect to demographic and baseline characteristics and safety

NOVUM PHARMACEUTICAL RESEARCH SERVICES
STATISTICAL ANALYSIS PLAN

Ketoconazole Cream 2%

Protocol / Study No. 71875502

variables.

For categorical variables, the number and percent of each category within a parameter will be calculated. For continuous variables, statistics will include n, mean, standard deviation, median and range.

All statistical analyses will be conducted using SAS®, Version 9.4 or higher. Datasets will be prepared using headings from Clinical Data Interchange Consortium (CDISC) Study Data Tabulation Model (SDTM) implementation for human clinical trials and ADaM (Analysis Dataset Model) and FDA Guidance of Technical Specifications - Comparative Clinical Endpoints Bioequivalence Study Analysis Datasets for Abbreviated New Drug Application (September 2018) .

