8.3 Safety Analysis

8.3.1 Adverse Events

All the adverse events (AEs) reported throughout the study will be coded and classified according to the MedDRA (Medical Dictionary for Regulatory Activities) coding dictionary (Version 21.0 or higher).

Treatment emergent adverse events (TEAE) are those that have a start date after the study treatment has been administered or the events that were present before administration of study treatment and worsen in severity after administration of study treatment. Treatment emergent adverse events will be summarized and analyzed in a summary table. Pre-treatment adverse events will be presented in the listing.

A summary table of the number and percent of patients with TEAEs by system organ class, preferred term, and treatment will be presented. Each patient will be counted only once within each preferred term.

A frequency summary table of the number of TEAEs by system organ class, preferred term, severity, and treatment will be presented. Severity will be classified as “Mild”, “Moderate”, or “Severe”.

Similarly, a frequency summary table of the number of TEAEs by system organ class, preferred term, and relationship to a study drug, and treatment will be presented. Relationship to a study drug will be classified as “Not Related” or “Related”.

If sufficient data exist, then TEAE frequencies will be compared among the three treatments using Fisher’s exact test; if this test is statistically significant at the 5% significance level, then a pairwise Fisher’s exact test comparing Test and Reference will be conducted.

TEAEs will be listed by treatment group and patient. Pre-treatment adverse events will be listed by patient.

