Patients with at least one AE	xxx (xx.x)	xxx (xx.x)	xxx (xx.x)	xxx (xx.x)
Discontinued study product due to above AE	xxx (xx.x)	xxx (xx.x)	xxx (xx.x)	xxx (xx.x)
AEs reported	Xxx	xxx	xxx	xxx
Mild	xxx (xx.x)	xxx (xx.x)	xxx (xx.x)	xxx (xx.x)
Moderate	xxx (xx.x)	xxx (xx.x)	xxx (xx.x)	xxx (xx.x)
Severe	xxx (xx.x)	xxx (xx.x)	xxx (xx.x)	xxx (xx.x)
Not Related	xxx (xx.x)	xxx (xx.x)	xxx (xx.x)	xxx (xx.x)
Related	xxx (xx.x)	xxx (xx.x)	xxx (xx.x)	xxx (xx.x)
Death	xxx (xx.x)	xxx (xx.x)	xxx (xx.x)	xxx (xx.x)
Serious AE	xxx (xx.x)	xxx (xx.x)	xxx (xx.x)	xxx (xx.x)

Test: Ketoconazole Cream 2% (Encube Ethicals Pvt Ltd)

Reference: Ketoconazole Cream 2% (G&W Laboratories Inc.; Registrant: Teva Pharmaceuticals USA Inc.)

Placebo: Placebo Cream (Test vehicle) (Encube Ethicals Pvt Ltd)

MedDRA Version 21.0

PROGRAM: L:\DEV\755\71875502\SAS\PGM\XXXX

Created on: ddmmmyy hh:mm

OUTPUT: L:\DEV\755\71875502\SAS\OUT\XXXX

Page 1 of N

NOVUM PHARMACEUTICAL RESEARCH SERVICES
STATISTICAL ANALYSIS PLAN

Ketoconazole Cream 2%

Protocol / Study No. 71875502

T14.3.2 Summary of Frequency of Adverse Events by Body System
(Safety Population)

Body System	Preferred Term	Test N = xxx		Reference N = xxx		Placebo N = xxx		Overall Fisher's P-value	Fisher's P-value Test vs. Reference
		Events	Patients n (%)	Events	Patients n (%)	Events	Patients n (%)		
Patients with at least one AE	Total	xx	xxx (xx.x)	xx	xxx (xx.x)	xx	xxx (xx.x)	0.1234	NA
Ear and labyrinth disorders etc.	Ear pain	xx	xxx (xx.x)	xx	xxx (xx.x)	xx	xxx (xx.x)	0.0425	0.0372

etc.

Test: Ketoconazole Cream 2% (Encube Ethicals Pvt Ltd)

Reference: Ketoconazole Cream 2% (G&W Laboratories Inc.; Registrant: Teva Pharmaceuticals USA Inc.)

Placebo: Placebo Cream (Test vehicle) (Encube Ethicals Pvt Ltd)

N = number of patients in safety population in that particular group; n= number of patients with data available for that particular group; total % is based on N

MedDRA Version 21.0

Note to programmer: If the global Fisher's exact test is statistically significant among the three treatment groups at the 5% alpha level (i.e. p < 0.05), then Fisher's exact test using only the test and reference groups will be performed to identify any potential statistically significant differences that are clinically relevant between the two active treatment groups.

PROGRAM: L:\DEV\755\71875502\SAS\PGM\XXXX
 Created on: ddmmmyy hh:mm

OUTPUT: L:\DEV\755\71875502\SAS\OUT\XXXX
 Page 1 of N

NOVUM PHARMACEUTICAL RESEARCH SERVICES
STATISTICAL ANALYSIS PLAN

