Treatment Group	Patient Screening Number	Patient Randomization Number	Visit	Evaluator	Erythema	Scaling	Pruritus	Fissuring/ Cracking	Maceration	Burning/ stinging	Total Severity	Clinical Cure/ Failure
	Test	xx-XXX	XXXX	1	xxx	0	0	0	1	0	0	1
Reference Placebo				2	xxx	0	0	0	1	0	0	1
				3	xxx	0	0	0	1	0	0	1
												Cure

Test: Ketoconazole Cream 2% (Encube Ethicals Pvt Ltd)

Reference: Ketoconazole Cream 2% (G&W Laboratories Inc.; Registrant: Teva Pharmaceuticals USA Inc.)

Placebo: Placebo Cream (Test vehicle) (Encube Ethicals Pvt Ltd)

PROGRAM: L:\DEV\755\71875502\SAS\PGM\XXXX

Created on: ddmmmyy hh:mm

OUTPUT: L:\DEV\755\71875502\SAS\OUT\XXXX

Page 1 of N

NOVUM PHARMACEUTICAL RESEARCH SERVICES
STATISTICAL ANALYSIS PLAN

Ketoconazole Cream 2%

Protocol / Study No. 71875502

L16.2.6.2 Listing of Mycological Culture and KOH Wet Mount Results

Treatment Group	Patient Screening Number	Patient Randomization Number	Visit	Mycological Culture	KOH Wet Mount	Mycological Cure/Failure	Therapeutic Cure/Failure
Test	xx-xxx	xxxx	1	T. rubrum/E. floccosum	Positive	Cure	Cure
			2	T. rubrum/E. floccosum	Negative		
			3	Negative	Negative		
	xx-xxxx		1	T. rubrum	Positive	Failure	Failure
			2	T. rubrum	Negative		
			3	T. rubrum	Negative		
Reference							
Placebo							

Test: Ketoconazole Cream 2% (Encube Ethicals Pvt Ltd)

Reference: Ketoconazole Cream 2% (G&W Laboratories Inc.; Registrant: Teva Pharmaceuticals USA Inc.)

Placebo: Placebo Cream (Test vehicle) (Encube Ethicals Pvt Ltd)

PROGRAM: L:\DEV\755\71875502\SAS\PGM\XXXX

Created on: ddmmmyy hh:mm

OUTPUT: L:\DEV\755\71875502\SAS\OUT\XXXX

Page 1 of N

NOVUM PHARMACEUTICAL RESEARCH SERVICES
STATISTICAL ANALYSIS PLAN

Ketoconazole Cream 2%

Protocol / Study No. 71875502

L16.2.7.1 Listing of Treatment Emergent Adverse Events by Treatment

Treatment Group	Patient Screening Number	Patient Randomization Number	Body System / MedDRA Term / AE Term	Treatment Area	Start /End Date/ Ongoing	Severity	Relationship to Study Drug	Outcome	Action Taken/ Other Action Taken	SAE
Test	xx-xxx	xxxx	Nervous system disorders / Headache / Headache	No	mm/dd/yyyy / mm/dd/yyyy	Mild	Related	Recovered	Dose Not Changed/ None	No

Reference
Placebo

Test: Ketoconazole Cream 2% (Encube Ethicals Pvt Ltd)

Reference: Ketoconazole Cream 2% (G&W Laboratories Inc.; Registrant: Teva Pharmaceuticals USA Inc.)

Placebo: Placebo Cream (Test vehicle) (Encube Ethicals Pvt Ltd)

PROGRAM: L:\DEV\755\71875502\SAS\PGM\XXXX
Created on: ddmmmyy hh:mm

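### The adverse event listings carry a treatment-area field, but no planned AE table or test shows how many patients per arm had an event there

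*SAP*

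**What the plan says.** **Where the field appears.** In SAP section 9, "L16.2.7.1 Listing of Treatment Emergent Adverse Events by Treatment" has a column headed "Treatment Area", filled in per event. The pre-treatment listing L16.2.7.2 has the same column.

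**How AEs are summarised.** SAP 8.3.1 states: "A summary table of the number and percent of patients with TEAEs by system organ class, preferred term, and treatment will be presented". It counts each patient once within a preferred term. Two further tables count events by severity and by relationship. None of T14.3.1 to T14.3.5 has a treatment-area row or column.

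**How AEs are tested.** SAP 8.3.1: "If sufficient data exist, then TEAE frequencies will be compared among the three treatments using" Fisher's exact test. A Test against Reference Fisher test follows only if the three-arm test is significant. The shell "T14.3.2 Summary of Frequency of Adverse Events by Body System" repeats this gate ("Note to programmer: If the global Fisher's exact test is statistically significant among the three treatment groups at the 5% alpha level") and shows the tests on the any-AE row and on a preferred-term row. The general level is in SAP 8: "If not otherwise specified, statistical significance is defined as $p < 0.05$ and is two-tailed". SAP 8.4 makes no multiplicity adjustment.

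**Why location matters.** Protocol 8.3: "Ketoconazole is not considered to be sufficiently absorbed from the skin to provide measurable systemic concentrations". The third objective in both documents is a safety comparison of the three products.

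**The concern.** For a cream with no measurable systemic exposure, a safety difference between Test and Reference would be expected mainly where the cream is applied. The natural safety count is patients per arm with at least one treatment-area event, and the planned tables do not give it.

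It cannot be rebuilt from them either. One patient may appear under several preferred terms, so patients cannot be summed across rows. Each term row also mixes events in the treatment area with the same term elsewhere on the body, and the any-AE row mixes local reactions with everything unrelated. A real Test excess could therefore be thinned across term rows and diluted in the any-AE row.

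**Working it through.** **Figures in the plan.** The documents give no power for any AE comparison. The randomised numbers do follow from their inputs: 332 + 332 + 166 = 830, and 540/(1 - 0.35) = 830.8, against 830 stated. The main stated power also reproduces: 172 per arm, 50% against 45%, a 20-point margin and the Yates term give 84.8%, against about 85%.

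**Inputs.**
- From the SAP: 332:332:166 (section 5), taken as an upper bound for the Safety population; three-arm Fisher p < 0.05, then Test against Reference Fisher p < 0.05 (8.3.1 and T14.3.2); two-sided 5% (section 8).
- Assumed, because neither document gives them: local reaction rates, number and spread of preferred terms, and the share of patients with unrelated AEs.

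**A worked example.** Take 20/332 Test and 7/332 Reference patients with a treatment-area event, and 3/166 on Placebo.
- Pooled row: three-arm p = 0.014, pairwise p = 0.017. The difference is 6.0% - 2.1% = 3.9 points. SE = sqrt(0.0602 × 0.9398/332 + 0.0211 × 0.9789/332) = 0.0153, so the 95% Wald CI is 3.9 ± 1.96 × 1.53, or 0.9 to 6.9 points.
- One of several term rows: 5 against 2 gives pairwise p = 0.45; 4 against 1 gives 0.37.
- An any-AE row of 80, 68 and 34 patients: three-arm p = 0.48.
- A single term row needs 8 against 1 (p = 0.038; 7 against 1 gives 0.069) or 10 against 2 (p = 0.037; 9 against 2 gives 0.063).

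The plan looks at every term row and the any-AE row, so one term row overstates the loss. The simulation takes them all together.

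**Simulation of the gated procedure.** Each patient with a local reaction has it under one term. A trial is flagged under the plan if any term row or the any-AE row passes both tests.

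| Local rates T/R/P | Terms | Unrelated AEs | Planned rows | One pooled row |
|---|---|---|---|---|
| 6/2/2% | 3 equal | 10% | 55% | 67% |
| 6/2/2% | 4 equal | 10% | 47-49% | 67-68% |
| 6/2/2% | 6 equal | 10% | 36% | 68% |
| 6/2/2% | one term holds 70% | 10% | 55% | 66% |
| 5/2/2% | 4 equal | 10% | 30% | 45% |
| 6/2/2% | 2 equal | 20% | 57% | 66% |
| 6/2/2% | 5 equal | 20% | 36% | 66% |
| 8/3/3% | 5 equal | 20% | 51% | 73% |
| 10/5/5% | 5 equal | 20% | 46% | 59% |
| Test 3%, Reference 2% | 4 equal | 10% | 7% | 7% |
| 3/3/3% (no difference) | 4 equal | 10% | 5% | 2% |

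The last line counts false flags in either direction. If all reactions fall under one term, that term row equals the pooled row and nothing is lost.

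**The case against.** **Many local symptoms are not AEs here.** Pruritus, erythema and burning/stinging are scored disease signs and symptoms. Protocol 11.8 keeps them out of the AEs unless they worsen so far that stopping and alternative therapy are judged best for the patient; Protocol 10.7 sets the bar at clinical significance. This stands. It makes a 6% AE rate less certain, and no table row can recover events that were never recorded as AEs.

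**Partial views exist.** T14.3.1 gives related events by arm over all terms, T14.3.3 has a total row split by relationship, and SAP 8.3.3 tabulates signs and symptoms by visit. If systemic exposure is negligible, related events should be largely local, so an excess could show there. This also stands in part. However, the relationship counts are of events rather than patients, depend on the investigator's causality judgement and are untested. The 8.3.3 table holds disease scores, also untested.

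**The field is thinly documented.** Neither document defines it. The shells show only the value No, so a yes/no coding for every event is an inference, and the casebook is not among the documents.

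**No efficacy conclusion depends on it.** Equivalence and superiority rest on the primary endpoint alone, and AE tests run only if data suffice. That limits the weight of the point but does not answer the third objective. The shells may be modified after analysis, and the count could be made from the listing, but a row chosen after seeing the data would be post hoc.

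**A stronger reading.** A reader might infer that a Test excess is likely to be missed. The documents do not support that: they give no reaction rates or coding spread. Under the assumptions above, the planned rows flag a 6% against 2% excess in roughly a third to more than half of trials, and the pooled row itself misses about a third.

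**Conclusion.** The gap is real: the listings carry a location field, and no planned AE summary or test uses it. The report would therefore omit the patient count most relevant to a topical product's safety comparison.

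The cost in sensitivity is conditional. At 6/2/2% with 10% unrelated AEs it is about 20 percentage points with four equal terms, about 11 with one dominant term, and more with six terms. It is nil with a single term or a difference as small as 3% against 2%. These figures rest on assumed rates, one term per reacting patient, no unrelated events under the same terms, and a Safety population close to 830; a smaller one would lower the detection rates. The pooled row makes a local difference easier to see but does not guarantee detection.

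**What to change.** Before unblinding, amend SAP 8.3.1, T14.3.1 and T14.3.2:

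- Define the treatment-area field and its permitted values, checked against the casebook.
- Add a row for patients with at least one TEAE in the treatment area: n and % of the Safety population by arm, broken down by preferred term.
- Apply the existing gated Fisher test to that row, and report the Test minus Reference difference with its 95% CI.
- Keep all existing AE tables. The new row need not be named the main AE comparison.
- Note beside it that Protocol 11.8 keeps most tinea-like symptoms out of the AEs, so the row is read together with the SAP 8.3.3 table.

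The cost is SAP wording and one row or sub-table from a field already in the shells, with no new data, visits or patients. The downside is one more AE p-value to interpret in a plan without multiplicity adjustment.

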11.8 Safety Analysis

Adverse events (AEs) will be classified using standard Medical Dictionary for Regulatory Activities (MedDRA) terminology Version 21.0 or higher and summarized by treatment group. Summary tables comparing the type, date of onset, date of resolution, incidence, severity, relationship to the study product, outcome, and action taken will be prepared by treatment group. If sufficient data exist, then AE frequencies will be compared among the three treatments using Fisher's exact test; if this test is statistically significant at the 5% significance level, then a pairwise Fisher's exact test comparing Test and Reference will be conducted.

CONFIDENTIAL PROTOCOL

A Randomized, Double-Blind, Vehicle-Controlled, Parallel-Design, Multiple-Site Clinical Study to Evaluate the Therapeutic Equivalence of Ketoconazole Cream 2% (Encube Ethicals Pvt Ltd) to Ketoconazole Cream 2% (G&W Laboratories Inc.) in the Treatment of Tinea Pedis

Signs and symptoms of tinea pedis will not be considered AEs, unless in the Investigator's opinion, they have increased in frequency and/or severity to such an extent that the Investigator/patient considers that it is in the patient's best interest to be discontinued from further participation in the study and given alternative therapy for their condition.

Concomitant medication use will be tabulated by patient.

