Ketoconazole Cream 2%

Protocol / Study No. 71875502

**T14.3.3 Summary of Frequency of Adverse Events by Relationship
(Safety Population)**

Body System	MedDRA Term	Test		Reference		Placebo			
		# of Events (N = xxx)	Related n (%)	Not Related n (%)	# of Events (N = xxx)	Related n (%)	Not Related n (%)	# of Events (N = xxx)	Related n (%)
Total AEs	Total	xx (xx.x)	xx (xx.x)	xx (xx.x)	xx (xx.x)	xx (xx.x)	xx (xx.x)	xx (xx.x)	xx (xx.x)
Ear and labyrinth disorders	Ear pain	xx (xx.x)	xx (xx.x)	xx (xx.x)	xx (xx.x)	xx (xx.x)	xx (xx.x)	xx (xx.x)	xx (xx.x)
	Hypoacusis	xx (xx.x)	xx (xx.x)	xx (xx.x)	xx (xx.x)	xx (xx.x)	xx (xx.x)	xx (xx.x)	xx (xx.x)

Test: Ketoconazole Cream 2% (Encube Ethicals Pvt Ltd)

Reference: Ketoconazole Cream 2% (G&W Laboratories Inc.; Registrant: Teva Pharmaceuticals USA Inc.)

Placebo: Placebo Cream (Test vehicle) (Encube Ethicals Pvt Ltd)

N = Total number of events in that particular group; Percentage is based on total number of events.

MedDRA Version 21.0

PROGRAM: L:\DEV\755\71875502\SAS\PGM\XXXX
Created on: ddmmmyy hh:mm

OUTPUT: L:\DEV\755\71875502\SAS\OUT\XXXX
Page 1 of N

NOVUM PHARMACEUTICAL RESEARCH SERVICES
STATISTICAL ANALYSIS PLAN

Ketoconazole Cream 2%

Protocol / Study No. 71875502

**T14.3.4 Summary of Frequency of Adverse Events by Severity
(Safety Population)**

Body System	MedDRA Term	Test			Reference			Placebo		
		Mild n (%)	Moderate n (%)	Severe n (%)	Mild n (%)	Moderate n (%)	Severe n (%)	Mild n (%)	Moderate n (%)	Severe n (%)
Total AEs	Total	xx (xx.x)	xx (xx.x)	xx (xx.x)	xx (xx.x)	xx (xx.x)	xx (xx.x)	xx (xx.x)	xx (xx.x)	xx (xx.x)
Ear and labyrinth disorders	Ear pain	xx (xx.x)	xx (xx.x)	xx (xx.x)	xx (xx.x)	xx (xx.x)	xx (xx.x)	xx (xx.x)	xx (xx.x)	xx (xx.x)
	Hypoacusis	xx (xx.x)	xx (xx.x)	xx (xx.x)	xx (xx.x)	xx (xx.x)	xx (xx.x)	xx (xx.x)	xx (xx.x)	xx (xx.x)

Test: Ketoconazole Cream 2% (Encube Ethicals Pvt Ltd)

Reference: Ketoconazole Cream 2% (G&W Laboratories Inc.; Registrant: Teva Pharmaceuticals USA Inc.)

Placebo: Placebo Cream (Test vehicle) (Encube Ethicals Pvt Ltd)

N = Total number of events in that particular group; Percentage is based on total number of events.

MedDRA Version 21.0

PROGRAM: L:\DEV\755\71875502\SAS\PGM\XXXX

Created on: ddmmmyy hh:mm

OUTPUT: L:\DEV\755\71875502\SAS\OUT\XXXX

Page 1 of N

NOVUM PHARMACEUTICAL RESEARCH SERVICES
STATISTICAL ANALYSIS PLAN

Ketoconazole Cream 2%

Protocol / Study No. 71875502

**T14.3.5 Summary of Frequency of Serious Adverse Events
(Safety Population)**

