Body System	Preferred Term	Test # Events	Reference # Events	Reference # Events
Injury, poisoning and procedural complications	Alcohol poisoning	xxx	xxx	xxx

Test: Ketoconazole Cream 2% (Encube Ethicals Pvt Ltd)

Reference: Ketoconazole Cream 2% (G&W Laboratories Inc.; Registrant: Teva Pharmaceuticals USA Inc.)

Placebo: Placebo Cream (Test vehicle) (Encube Ethicals Pvt Ltd)

MedDRA Version 21.0

PROGRAM: L:\DEV\755\71875502\SAS\PGM\XXXX
Created on: ddmmmyy hh:mm

OUTPUT: L:\DEV\755\71875502\SAS\OUT\XXXX
Page 1 of N

NOVUM PHARMACEUTICAL RESEARCH SERVICES
STATISTICAL ANALYSIS PLAN

Ketoconazole Cream 2%

Protocol / Study No. 71875502

**T14.3.6 Summary of Vital Signs
(Safety Population)**

Vital Signs	Visit	Statistic	Test N = xxx	Reference N = xxx	Placebo N = xxx	
Systolic Blood Pressure (mmHg)	Visit 1	n	xxx	xxx	xxx	
		Mean \pm SD	xxx.x \pm xx.x	xxx.x \pm xx.x	xxx.x \pm xx.x	
		Median	xxx.x	xxx.x	xxx.x	
		Range	xxx.x – xxx.x	xxx.x – xxx.x	xxx.x – xxx.x	
Visit 2						
Visit 3/Early Termination						
Diastolic Blood Pressure (mmHg)						
Pulse Rate (beats/min)						
Respiration Rate (breaths/min)						
Temperature (F)						

Test: Ketoconazole Cream 2% (Encube Ethicals Pvt Ltd)

Reference: Ketoconazole Cream 2% (G&W Laboratories Inc.; Registrant: Teva Pharmaceuticals USA Inc.)

Placebo: Placebo Cream (Test vehicle) (Encube Ethicals Pvt Ltd)

N = Total number of events in that particular group; Percentage is based on total number of events.

PROGRAM: L:\DEV\755\71875502\SAS\PGM\XXXX
Created on: ddmmmyy hh:mm

OUTPUT: L:\DEV\755\71875502\SAS\OUT\XXXX
Page 1 of N

NOVUM PHARMACEUTICAL RESEARCH SERVICES
STATISTICAL ANALYSIS PLAN

Ketoconazole Cream 2%

Protocol / Study No. 71875502

L16.2.1 Listing of Discontinued Patients

Treatment Group	Patient Screening Number	Patient Randomization Number	Discontinuation Reason	Population
Test	xx-XXX xx-XXX	xxxx xxxx	Withdrawal by Patient Lost to Follow-up	Per-Protocol Safety
Reference Placebo				

Test: Ketoconazole Cream 2% (Encube Ethicals Pvt Ltd)

Reference: Ketoconazole Cream 2% (G&W Laboratories Inc.; Registrant: Teva Pharmaceuticals USA Inc.)

Placebo: Placebo Cream (Test vehicle) (Encube Ethicals Pvt Ltd)

PROGRAM: L:\DEV\755\71875502\SAS\PGM\XXXX

Created on: ddmmmyy hh:mm

OUTPUT: L:\DEV\755\71875502\SAS\OUT\XXXX

Page 1 of N

NOVUM PHARMACEUTICAL RESEARCH SERVICES
STATISTICAL ANALYSIS PLAN

Ketoconazole Cream 2%

Protocol / Study No. 71875502

L16.2.2 Listing of Protocol Deviations

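### The SAP's AE tables by relationship and severity give shares of events, and no table clearly gives the number and percent of patients with a related or a severe event

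*SAP*

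**What the plan says.** SAP section 8.3.1 plans three kinds of adverse-event table. The first is at patient level: "A summary table of the number and percent of patients with TEAEs by system organ class, preferred term, and treatment will be presented". The other two count events. For severity: "A frequency summary table of the number of TEAEs by system organ class, preferred term, severity, and treatment will be presented". The relationship table is planned in the same way, as a count of events.

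The shells in SAP section 9 follow this split:

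- **T14.3.2** (body system and preferred term) shows events and patients n (%) over the Safety population. It has a three-arm Fisher p-value and, if that is significant, a Test versus Reference p-value. It is not split by relationship, severity or seriousness.
- **T14.3.3 and T14.3.4** ("T14.3.3 Summary of Frequency of Adverse Events by Relationship" and "T14.3.4 Summary of Frequency of Adverse Events by Severity") both carry the footnote "N = Total number of events in that particular group; Percentage is based on total number of events".
- **T14.3.1** (overall summary) has n (%) rows for mild, moderate, severe, related, not related, death and serious AE. No footnote says whether these are patients or events. The severity and relationship rows stand beneath the row for AEs reported, which suggests events.
- **T14.3.5** (serious events) has the columns "Test # Events Reference # Events Reference # Events". It shows no patients, no percentage and no N, and no column is headed Placebo.

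Protocol section 11.8 calls for "Summary tables comparing the type, date of onset, date of resolution, incidence, severity, relationship to the study product, outcome, and action taken", by treatment group. The third study objective is to compare the safety of the three products.

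**The concern.** A percentage in a three-arm safety table is normally read as risk: of the patients given this product, how many had the event. In T14.3.3 and T14.3.4 it means something else: of the events reported in this arm, what share were related, or severe. That share does not depend on how many patients were treated or how many were affected. It stays fixed when every kind of event rises in proportion, and one patient with repeated events can move it. It is therefore not a quantity on which the arms can be compared.

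T14.3.5 has a different weakness. It has no percentage at all, and under 2:2:1 allocation a bare count means different things in an active arm and in Placebo. Nor does it separate several patients from one patient with several events.

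At stake is whether the report can answer a plain question under the safety objective: how many patients on each product had a related, a severe or a serious event?

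**Working it through.** The documents state no expected adverse-event rates, so there is no figure of theirs to reproduce. The check compares the planned percentage with the patient-based one on assumed counts.

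**Inputs.** Arm sizes are 332, 332 and 166 (Protocol 11.2, SAP 5). Assumed: every randomized patient is in the Safety population, and the event counts are as given below.

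**Formulas.** Planned: events in the category / all events in the arm. Patient-based: patients with such an event / Safety N of the arm.

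**1. Proportional excess.** Test has 40 related of 80 events; Reference has 20 of 40. No patient has more than one related event.
- Planned: 40/80 = 50.0% and 20/40 = 50.0%.
- Patient-based: 40/332 = 12.0% and 20/332 = 6.0% (two-sided Fisher's exact p = 0.0096).

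**2. Disproportionate excess.** Test has 20 related of 120 events; Reference has 10 of 40. No patient has more than one related event.
- Planned: 20/120 = 16.7% and 10/40 = 25.0%, so Test looks better.
- Patient-based: 20/332 = 6.0% and 10/332 = 3.0%, so Test has double the rate.

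**3. Serious events.** There are 4 events in an active arm and 4 in Placebo, one per patient. T14.3.5 prints 4 and 4. The rates are 4/332 = 1.2% and 4/166 = 2.4%.

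**4. What T14.3.2 would show for example 1.**
- If each affected patient has exactly one event: 80/332 = 24.1% against 40/332 = 12.0% (p = 0.00007).
- If each affected patient has one related and one unrelated event: 40/332 = 12.0% against 20/332 = 6.0% (p = 0.0096).
- The pairwise p-value is printed only if the three-arm test is significant. With Placebo assumed anywhere from 5/166 (3.0%) to 40/166 (24.1%), an approximate three-arm chi-square gives p of at most 0.0003 in the first case and 0.026 in the second, so it would be printed.

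Steps 1 and 2 show that the planned percentage does not track risk. Step 4 shows that the overall excess would still be seen elsewhere.

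**The case against.** A reader might infer that these tables could conceal an excess of related or severe events on Test. The documents do not support that.

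- The raw count stands beside every percentage in T14.3.3 and T14.3.4, and T14.3.3 also prints the arm's event total. The two active arms are planned at equal size, so 40 against 20 is plain to see.
- Equal percentages need total events to rise in proportion, and T14.3.2 is the table that picks up an overall rise, as step 4 shows.
- The only formal comparison of adverse events is Fisher's test, and T14.3.2 reports it alongside patient counts. T14.3.3 and T14.3.4 carry no p-value and can be taken as descriptive.
- T14.3.1 has a serious AE row with n (%), and listing L16.2.7.1 gives every treatment-emergent event by patient with severity, relationship and a serious flag.
- SAP section 9 says that headers and footnotes will be modified as needed, and the repeated Reference heading is evidently a slip. Protocol 11.8 does not demand patient incidence split by severity or relationship.

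All of this stands, and it limits the consequence. It does not close the gap. T14.3.2 cannot say whether an excess is related or severe. Event counts cannot tell many patients from one patient with repeats. The T14.3.1 rows have no stated denominator, and a listing is not a tabulated comparison. The allowance for changing shells does not reach SAP 8.3.1, which itself plans event counts for these tables.

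**Conclusion.** The point holds as a minor reporting weakness. The percentages in T14.3.3 and T14.3.4 describe the mix of events and are not comparable between arms as risks. No table clearly gives the number and percent of patients with a related or a severe treatment-emergent event. T14.3.1 leaves its severity, relationship and serious-event denominators undefined. T14.3.5 lacks patients and N in a 2:2:1 trial and heads its third column Reference.

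The size shown, identical 50.0% against 12.0% and 6.0% of patients, rests on assumed counts, no more than one related event per patient and full inclusion in the Safety population. That the planned percentage does not respond to proportional scaling needs none of these assumptions. The equivalence and superiority analyses are not affected.

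**What to change.** - **T14.3.3 and T14.3.4:** add patients n (%) with the arm's Safety population as N. Count each patient once per preferred term, at the worst severity and the strongest relationship. Keep event counts in a separate column.
- **T14.3.5:** add patients n (%) over the Safety N, and head the third column Placebo.
- **T14.3.1:** state for the severity, relationship, death and serious AE rows whether they count patients or events, and over which denominator.
- **SAP 8.3.1:** for the severity and relationship tables, plan the number and percent of patients as well as the number of events.
- **T14.3.6:** remove the event-based footnote from this vital-signs table, where it cannot apply.

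The cost is SAP wording, a few shell edits, a little more programming and slightly larger tables. No new data are needed, since L16.2.7.1 already calls for severity, relationship and the serious flag by patient.
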